Abbreviations: AE, adverse event; BMS, Bristol-Myers Squibb; C, cycle; CLIA, Clinical Laboratory Improvements Amendments; CT, computed tomography; D, day; DNA, deoxyribonucleic acid; ECG, electrocardiogram; ECOG, Eastern Cooperative Oncology Group; FSH, follicle stimulating hormone; HCV, hepatitis C virus; HCC, hepatocellular carcinoma; HIV, human immunodeficiency virus; IgG, immunoglobulin G; IRT, Interactive Response Technology; MRI, magnetic resonance imaging; PCR, polymerase chain reaction; PE, physical examination; RNA, ribonucleic acid; SAE, serious adverse events; SARS-CoV-2, severe acute respiratory syndrome coronavirus 2; WOCBP, women of childbearing potential,

^a There will be a 72 hour window at screening prior to C1D1 for the collection of laboratory tests,

Protocol Amendment No: 04
Date:06-Jan-2022

Table 2-2: On Treatment - Schedule of Activities - q2w and q4w Dosing - Cycles 1 to 3 (Parts 1A, 1B, 2A, and 2B)

Procedure	Cycle 1								Cycles 2 to 3								EOT ^{a, b}
	D1	D2	D5	D8	D15	D22	D29	D43	D1	D2	D5	D8	D15	D29	D43		
Safety Assessments																	
ECOG Performance Status	X																
PE	X								X							X	
Symptom Directed PE				X	X	X	X	X					X	X	X		
Weight	X				X		X	X	X					X			
Vital Signs ^c	X			X	X	X	X	X					X	X	X		
Oxygen Saturation ^c	X				X												
ECGs ^d	X					X		X						X		X	
Laboratory Tests ^e	X			X	X ^k	X	X	X ^k	X				X ^k	X	X ^k		
Urinalysis	As clinically indicated; microscopic urine reflex only for urinalysis positive for blood/protein/leukocyte esterase																
Pregnancy Test (WOCBP only) ^f	X				X		X	X	X				X	X	X	X	
Adverse Event Reporting																	
Monitor for Non-Serious Adverse Events (Appendices 3 and 4)	X	Non-Serious AEs will be collected starting with the first dose of study medication and through 100 days following last dose of study drug.															
Monitor for Serious Adverse Events (Appendices 3 and 4)	X	All SAEs must be collected from the date of the participant's written consent until 100 days following the last dose of study drug.															
Concomitant Medications	X				X		X	X	X				X	X	X		
Pharmacokinetic (PK) Assessments																	
Serial Serum PK and Immunogenicity Sampling	See Table 9.5-2 and Table 9.5-3 of pharmacokinetic and immunogenicity sampling schedule and Section 9.5 .																

Table 2-2: On Treatment - Schedule of Activities - q2w and q4w Dosing - Cycles 1 to 3 (Parts 1A, 1B, 2A, and 2B)

Procedure	Cycle 1								Cycles 2 to 3								EOT ^{a, b}

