^b For participants who complete all scheduled cycles of therapy, the EOT visit will be the same as the last scheduled and completed on-treatment visit (eg, Cycle 3 Day 43) and the start of the safety follow-up period. For participants that do not complete all scheduled cycles of therapy, the EOT visit will be the most recent on-treatment visit (with all available safety and response data), does not need to be repeated and will be considered the start of the safety follow-up period.

^c Obtainment of vital signs surrounding study drug administration(s) from Cycle 2 on as per institutional practice/Investigator discretion.

^d ECGs should be recorded after the participant has been supine for at least 5 minutes, and prior to blood draws. Single safety ECGs to be done on Day 1 and Day 29 of all treatment cycles where ECG not performed in conjunction with PK sampling.

^e There will be a 72-hour window for collection of all laboratory tests. See [Section 9.4.4](#) and [Table 9.4.4-1](#).

^f Serum/urine to be collected within 24 hours prior to dosing. Pregnancy test may be completed on the first day of treatment provided the results are available before the start of study therapy. Serum or urine pregnancy test must be performed within 24 hours prior to administration of study drug (urine pregnancy test: minimum sensitivity 25 IU/L or equivalent units of hCG).

^g Same imaging modality to be used for all assessments, per RECIST v1.1 ([Appendix 5](#)). Tumor assessment to be performed prior to initiating next cycle of treatment. Unconfirmed PR/CR must be confirmed at least 4 weeks after initial assessment finding ([Section 9.4.5](#))

^h Study drugs, BMS-986207 and nivolumab, to be supplied by BMS; vials assigned by IRT should be used. In limited instances, scheduled drug administration can occur outside of the indicated timeframes but the Sponsor should always be notified first.

ⁱ Pregnancy testing on D15 and D43 time points only for q2w dosing.

Table 2-4: On Treatment- Schedule of Activities -Triplet Cohort (Part 1C) and Triplet NSCLC Expansion (Part 2C)

Procedure	Cycle 1 Visit Window = -3 Days for C1D1, ± 3 Days for All Others						Each Subsequent Cycle		EOT	Notes 1 Cycle = 6 weeks
	D1	D8	D15	D22	D29	D36	D1 (± 3 Days)	D22 (± 3 Days)		
Safety Assessments										
PE	X						X		X	
Physical Measurements	X			X			X	X		See Appendix 8 : For C1D21 and each subsequent cycle D1 and D21 weight only
Symptom-directed PE		X	X		X	X				To include signs and symptoms

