Vital Signs and Oxygen Saturation	X	X	X	X	X	X	X	X		
ECGs	X						X		X	ECGs should be recorded after the participant has been supine for at least 5 minutes, and prior to blood draws. Single safety ECGs to be done on Day 1 of all treatment cycles.
Adverse Event Assessments	Continuously during the study								All SAEs must be collected from the date of the participant's written consent until 100 days following the last dose of study drug. All AEs (including SAEs and non-serious AEs), including those associated with SARS-CoV-2 infection, must be collected continuously during the treatment period.	
Review of Concomitant Medications	X	X	X	X	X	X	X	X	X	

Table 2-4: On Treatment- Schedule of Activities -Triplet Cohort (Part 1C) and Triplet NSCLC Expansion (Part 2C)

Procedure	Cycle 1 Visit Window = -3 Days for C1D1, ± 3 Days for All Others						Each Subsequent Cycle		EOT	Notes 1 Cycle = 6 weeks
	D1	D8	D15	D22	D29	D36	D1 (± 3 Days)	D22 (± 3 Days)		
Pregnancy Test (WOCBP only)	X			X			X	X	X	For WOCBP; serum/urine pregnancy test to be performed (urine pregnancy test: minimum sensitivity 25 IU/L or equivalent units of hCG), see Section 9.2.5 .
ECOG Performance Status	X						X			Confirm status prior to randomization and on C1D1
Laboratory Assessments										
Chemistry and hematology tests	X			X			X	X		Within 72 hrs prior to dosing. See 9.4.4 and Table 9.4.4-1 .

Table 2-4: On Treatment- Schedule of Activities -Triplet Cohort (Part 1C) and Triplet NSCLC Expansion (Part 2C)

Procedure	Cycle 1 Visit Window = -3 Days for C1D1, ± 3 Days for All Others						Each Subsequent Cycle		EOT	Notes 1 Cycle = 6 weeks		
	D1	D8	D15	D22	D29	D36	D1 (± 3 Days)	D22 (± 3 Days)				
Efficacy Assessments												
Body Imaging	Contrast enhanced CT of the chest, CT/MRI of the abdomen, pelvis, and all other known and/or suspected sites of disease should occur every 6 weeks starting from date of first dose (± 7 days) for the first 12 months (week 48), then every 12 weeks (± 7 days) until the end of year 2, then every 12 weeks (± 14 days) thereafter until disease progression or treatment discontinuation, whichever occurs later. See Section 9.1 and Section 5.1.4 for further details.											

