- 2) Some of the assessments referred to in this section may not be captured as data in the eCRF. They are intended to be used as safety monitoring by the treating physician. Additional testing or assessments may be performed as clinically necessary or where required by institutional or local regulations.

Table 2-5: Follow-up Procedural Outline (All Participants)

Procedure	Safety Follow-up			Survival Follow-up	Response Follow-up ^a	Notes
	Follow-up 1 30 Days ^b (± 7 days)	Follow-up 2 60 Days (± 7 days)	Follow-up 3 100 Days (± 7 days)			
Safety Assessments						
Physical Examination	X	X	X			
Vital Signs	X	X	X			Includes body temperature, seated/supine blood pressure, and heart rate.
Laboratory Tests ^c	X	X	X			Lab tests also as clinically indicated; See laboratory assessments in Section 9.4.4 and Table 9.4.4-1
Urinalysis	As clinically indicated. See Section 9.4.4					
Pregnancy Test	X	X	X			For WOBCP; serum/urine pregnancy test to be performed (urine pregnancy test: minimum sensitivity 25 IU/L or equivalent units of hCG), (Section 9.2.5).
Adverse Event Reporting and Concomitant Medication Assessments						
Monitor for Non-Serious Adverse Events	X	X	X			Non-Serious AEs will be collected starting with the first dose of study medication and through 100 days after discontinuation of dosing (Appendices 3 and 4).

Table 2-5: Follow-up Procedural Outline (All Participants)

Procedure	Safety Follow-up			Survival Follow-up	Response Follow-up ^a	Notes
	Follow-up 1 30 Days ^b (± 7 days)	Follow-up 2 60 Days (± 7 days)	Follow-up 3 100 Days (± 7 days)			
Monitor for Serious Adverse Events	X	X	X	All Participants - Commence with Start of Safety Follow-up: Follow-up Every 12 Weeks until 2 Years After LAST Dose of Study Drug	Commences with Start of Safety Follow-up: Follow-up Done Every 12 Weeks for 1 Year After LAST Dose of Study Drug	All SAEs must be collected from the date of the participant's written consent until 100 days post discontinuation of dosing. Participants will be followed for all SAEs and all AEs (SAEs and non-serious AEs) associated with confirmed or suspected SARS-CoV-2 infection until resolution, the condition stabilizes, the event is otherwise explained, the event is deemed irreversible, the participant is lost to follow-up (as defined in Section 8.3), or for suspected cases, until SARS-CoV-2 infection is ruled-out.
Concomitant Medication Assessments	X	X	X			

Table 2-5: Follow-up Procedural Outline (All Participants)

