The potential benefit of combination immunotherapy of BMS-986207 plus nivolumab plus ipilimumab in first line treatment of NSCLC is not yet known. The safety profile of nivolumab and ipilimumab plus BMS-986207 is expected to have no new categories of AEs compared to BMS-986207 monotherapy, nivolumab monotherapy, ipilimumab monotherapy, or nivolumab plus ipilimumab combination therapy. The frequencies and intensities of these AEs in the nivolumab and ipilimumab plus BMS-986207 combination may be higher. Preliminary data of CA020002 Part 1C, as per 20-Oct-2021, revealed that 2 out of 4 DLT-evaluable participants experienced DLTs with the combination of BMS-986207 1200 mg Q3W, nivolumab 360 mg Q3W, and ipilimumab 1 mg/kg Q6W (Grade 3 encephalitis and Grade 3 bullous dermatitis, see [Section 3.2.1.4](#) for more details).¹⁹ Per BOIN design, BMS-986207 dose of 1200 mg Q3W was reduced to 600 mg due to the reported DLTs. If needed, BMS-986207 dosing will be further reduced in the setting of SAEs or worsening AE profiles. When BMS-986207 was combined with nivolumab, participants with melanoma (1 participant with a complete response [CR], 2 participants with partial response [PR]), and prostate cancer (1 participant with PR) experienced clinical benefit (unpublished results). When 1200 mg BMS-986207 was combined with nivolumab and ipilimumab (n = 6 treated participants), PR was observed in one participant with CRC and stable disease (SD) with NSCLC (post PD-1 therapy). No clinical benefit was observed in any participants who received BMS-986207 monotherapy (unpublished results). Other tumor types in this study included pancreatic, ovarian, breast, gastric, and urothelial cancer. In efforts to reduce toxicity associated with ipilimumab, a lower dose of 1 mg/kg at a 6-week dosing interval will be used. This dose of ipilimumab is currently approved for the treatment of 1L NSCLC in combination with nivolumab or with nivolumab and 2 cycles of chemotherapy.

Patients who develop immune-related AEs may require prolonged treatment with high dose corticosteroids and other immunosuppressive agents. This could increase the risk of opportunistic infections. Immune-related AE management algorithms in the protocol recommend antibiotic prophylaxis against opportunistic infections in such situations.

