The clinical studies of BMS-986207 have been designed to minimize the overall risk to participants. Complete blood counts and chemistry (including liver enzyme) tests will be carried out prior to administration of study therapy and on a weekly basis during the first 4 weeks of treatment. In addition, complete physical examinations (PEs) will be conducted on Day 1 of each new cycle, along with weekly symptom-directed targeted PEs during the first 4 weeks of treatment. Due to the potential risk of exaggerated inflammatory response, participants with auto-immune disorders, who are at risk for flare of auto-immunity, will be excluded.

Continuous safety assessments will be utilized by the Investigators and Sponsor to determine whether dose modification, additional safety measures, or termination of the study is required at any time. In addition, AEs and SAEs will be reviewed on an ongoing basis by the BMS Medical Monitor and World Wide Patient Safety (WWPS) representatives to monitor for any safety signals or trends. As BMS-986207 is an experimental agent, it is possible that unforeseen, unknown, or unanticipated reactions may occur. However, based on the nonclinical safety profile of BMS-986207, and with a 91-fold exposure margin built into the planned starting dose of 1 mg/kg (or 80 mg based an average body weight of 80 kg in cancer patients), the potential safety risks are expected to be minimized.

No additional safety monitoring or routine screening tests will be required due to the SARS-CoV-2 pandemic. Participants with recent or acute infections will be excluded or delay start of treatment as defined in [Section 6.2](#). If a participant has a confirmed SARS-CoV-2 infection while on study treatment, dose delay or interruption of study treatment is required as described in [Section 8.1](#).

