9. STUDY ASSESSMENTS AND PROCEDURES

- Study procedures and timing are summarized in the Schedule of Activities. Protocol waivers or exemptions are not allowed. Adherence to the study design requirements, including those specified in the Schedule of Activities, is essential and required for study conduct.
- Study governance considerations in terms of compliance and reporting of AEs are available in [Appendices 2 and 3](#).
- All screening evaluations must be completed and reviewed to confirm that potential participants meet all eligibility criteria before enrollment. The Investigator will maintain a screening log to record details of all participants screened and to confirm eligibility or record reasons for screening failure, as applicable.
- Procedures conducted as part of the participant's routine clinical management (eg, blood count) and obtained before signing of informed consent may be utilized for screening or baseline purposes provided the procedure meets the protocol-defined criteria and has been performed within the timeframe defined in the Schedule of Activities.
- All immediate safety concerns must be discussed with BMS immediately upon occurrence or awareness to determine if the participant should continue or discontinue treatment

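### Section 3.3 states weekly safety laboratories for the first 4 weeks, but Table 2-4 gives the triplet (Parts 1C/2C) only D1 and D22 in Cycle 1, so silent laboratory DLTs can be missed

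*Combined protocol and SAP*

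**What the plan says.** - **Section 3.3 (Benefit/Risk Assessment)** describes how the BMS-986207 studies limit risk. Blood counts and chemistry, including liver enzymes, "tests will be carried out prior to administration of study therapy and on a weekly basis during the first 4 weeks of treatment". The same paragraph adds physical examinations "along with weekly symptom-directed targeted PEs during the first 4 weeks of treatment". Neither statement is limited to particular Parts. The section also covers the triplet, reporting that Part 1C data at 1200 mg "revealed that 2 out of 4 DLT-evaluable participants experienced DLTs".
- **Table 2-4 (Parts 1C and 2C)** marks chemistry and haematology in Cycle 1 on D1 and D22 only, then on D1 and D22 of each later cycle. The row note reads "Within 72 hrs prior to dosing. See 9.4.4 and Table 9.4.4-1". Symptom-directed examinations ("To include signs and symptoms") are marked on D8, D15, D29 and D36. Note 2 to the table says "Additional testing or assessments may be performed as clinically necessary or where required by institutional or local regulations".
- **Table 2-2 (Parts 1A, 1B, 2A, 2B)** marks laboratory tests in Cycle 1 on D1, D8, D15, D22, D29 and D43.
- **Section 9** gives the schedule its force: "Adherence to the study design requirements, including those specified in the Schedule of Activities, is essential and required for study conduct".
- **Section 5.1.2.6** sets a 42-day DLT period for Part 1C and treats a dose as safe if at most 1 of the first 6 evaluable participants has a DLT. Part 2C may then start enrolling.

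**The concern.** The laboratory safeguard in Section 3.3 does not reach the triplet. Its companion in the same paragraph, the frequent symptom-directed examination, does appear in Table 2-4.

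Several DLTs in Section 7.4.1 can be met on laboratory values alone:
- Grade 4 AST, ALT, ALP or bilirubin, and Grade 4 thrombocytopenia, with no minimum duration.
- Grade 3 AST, ALT or ALP lasting more than 5 days.
- Grade 4 neutropenia lasting at least 7 days.

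Amylase or lipase rises without pancreatitis are excluded from the DLT definition, so they do not add to the exposure. The events at risk are drug-related laboratory DLTs without symptoms that begin and resolve between two draws. Missing them can only lower the DLT count, and that count decides whether a dose is called safe and whether Part 2C opens. Expansion to 18 participants does not cure this, because those participants follow the same draw schedule.

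**Working it through.** **1. Draw spacing, from the tables**

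| Source | Cycle 1 draws, then next | Gaps (days) |
|---|---|---|
| Table 2-2 | D1, 8, 15, 22, 29, 43 | 7, 7, 7, 7, 14 |
| Table 2-4 | D1, 22, C2D1 (= D43) | 21, 21 |

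Table 2-2 reproduces the weekly statement in Section 3.3. Table 2-4 does not.

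The windows widen this. Visits may move ±3 days (C1D1: up to 3 days early), and laboratories may precede dosing by 72 hours. The D1-to-D22 gap then runs from (22 − 3 − 3) − 1 = 15 to (22 + 3) − (1 − 3) = 27 days. The C2D1 draw can fall from D37 to D46, so D22 may be the only scheduled post-dose draw inside the 42-day DLT period.

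**2. Chance that a scheduled draw touches an event of d days**

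Onset is uniform. Model (a) lets the event start anywhere in the 42 days; model (b) requires it to lie wholly within D1-D43. The draws are D22 and D43 for Table 2-4, and D8, D15, D22, D29 and D43 for Section 3.3 (C2D1 kept). For Table 2-4, model (a) gives 2d/42 and model (b) gives d/(42 − d), each capped at 1. With d = 7 these are 14/42 = 33.3% and 7/35 = 20.0%.

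| d (days) | Table 2-4, (a) / (b) | Section 3.3, (a) / (b) |
|---|---|---|
| 6 | 28.6% / 16.7% | 71.4% / 66.7% |
| 7 | 33.3% / 20.0% | 83.3% / 80.0% |
| 14 | 66.7% / 50.0% | 100% / 100% |
| 21 or more | 100% / 100% | 100% / 100% |

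**3. Effect on the at-most-1-in-6 rule (illustration)**

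The true DLT rate is taken as 36%, the upper end of the interval stated with the 30% target in Section 5.1.2.6. A share s of DLTs is laboratory-only, with s = 10-30% **assumed**.

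Observed rate q = 0.36 × [1 − s × (1 − detection)], and P(X ≤ 1) = (1 − q)^6 + 6q(1 − q)^5.

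- Full ascertainment: q = 0.36, P = 0.301.
- Mildest 6-7 day case under Table 2-4 (d = 7, model a, s = 0.1): q = 0.36 × (1 − 0.1 × 0.667) = 0.336, P = 0.346.
- Worst case (d = 6, model b, s = 0.3): q = 0.36 × (1 − 0.3 × 0.833) = 0.270, P = 0.487.

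| Event duration | Table 2-4 | Section 3.3 draws |
|---|---|---|
| 6-7 days | 0.346-0.487 | 0.312-0.370 |
| 14 days | 0.323-0.407 | 0.301 |
| 21 days or more | 0.301 | 0.301 |

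With the same inputs in both columns, the schedules differ by about 3 to 14 percentage points for 6-7 day events. The smallest difference is 0.349 − 0.320 (d = 6, model a, s = 0.1) and the largest 0.479 − 0.341 (d = 7, model b, s = 0.3). For 14-day events the difference is 2 to 11 points.

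**4. Duration criteria need two draws**

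One draw shows an abnormality but not how long it lasted. Two scheduled draws fall inside a 6-7 day event 0% of the time under either schedule. For a 14-day event the figure is 0% under Table 2-4, against 21/42 = 50% (a) or 21/28 = 75% (b) under Section 3.3. Denser draws alone therefore do not settle the shorter duration-defined DLTs.

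**The case against.** The strongest reply is that the Section 3.3 sentence is older text for the monotherapy and doublet Parts. Section 5.1.2.1, which covers those Parts, sets weekly visits for the first 4 weeks; the parallel triplet section (5.1.2.2) does not. The paragraph after the laboratory statement relies on the exposure margin at the monotherapy starting dose. Table 2-4's examination days also differ from Table 2-2's, so the triplet schedule may have been built deliberately around q3w dosing. That is a plausible origin, but it does not remove the conflict. Section 3.3 was revised for the triplet in Amendment 03 and again in Amendment 04. It limits the sentinel safeguard to Parts 1A and 1B, yet leaves the laboratory statement without a limit. No rationale for thinner testing in the triplet was found.

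Second, sites face no ambiguity, because the schedule is binding. That is true, and it is why the sparser table is the one that will be followed.

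Third, other provisions help: extra testing as clinically necessary, dose holds for Grade 2 or higher AST, ALT or bilirubin (Section 7.4.3), AE follow-up (Section 9.2.3) and p-DILI retesting (Section 9.2.7). They matter once something prompts a test or a draw shows the abnormality. They do not reach a silent event between draws.

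Fourth, the magnitude rests on assumptions, and this stands. Both Part 1C DLTs reported so far were clinical (encephalitis and bullous dermatitis), so the laboratory-only share may be low. A 36% rate is the edge of the plan's own interval, so accepting a dose there is not clearly wrong. The 49% figure needs the largest share, the shortest duration and the more adverse onset model together; model (a) gives 46% for the same share and duration. Dose decisions also weigh the totality of data, and Part 2C has continuous Bayesian monitoring, though on the same draw schedule.

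**Conclusion.** The concern holds. The current text contradicts itself, and the binding schedule omits for the triplet a safeguard that Section 3.3 states without exception. The direction of any bias is certain: missed laboratory DLTs favour calling a dose tolerable. Its size is not known, because the documents give neither the laboratory-only share of DLTs nor their duration. Under the stated assumptions the effect on the 6-participant rule ranges from none (events of 21 days or more) to a rise from 30% to 49% in the chance of passing a dose with a 36% DLT rate. The inconsistency stands without those figures. This should be corrected; confidence is medium because the practical effect may be small.

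**What to change.** In Table 2-4, mark chemistry and haematology at C1 D8, D15 and D29, with D36 optional. Add a note to the row: any Grade 3-4 laboratory abnormality is repeated until its duration against the Section 7.4.1 criterion is known, for example within 3 business days, the retest interval Section 9.2.7 already sets for suspected p-DILI. The note is needed because the added draws alone cannot establish the duration of a 6-7 day event.

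If dosing-day testing is intended for the triplet, Section 3.3 should say so and justify it. That would remove the contradiction but leave the 21-day gaps.

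The cost is protocol wording plus three safety samples per participant in Cycle 1. These fall at visits that already exist and where Table 9.5-4 already draws PK blood. Repeat tests arise only when an abnormality is found.
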